We will pursue additional secondary analyses to investigate whether baseline measurements of the biomarkers (blood eosinophils, periostin, and exhaled nitric oxide) significantly predict any of these secondary outcomes. We will achieve this by including the biomarkers in the statistical models described in the previous paragraph.

Finally, we will perform exploratory subgroup analyses of the primary and secondary outcomes within levels of gender, minority status, age group, baseline BMI, and baseline FEV_1 .

E. Missing Data

Because of the possibility of drop-outs and other missed visits, there will be some missing data. The statistical models and analyses that are planned for the

primary and secondary outcomes assume that the data are missing-at-random (MAR). Because we are applying likelihood-based methods for the data adjustment with primary outcome and for all of the secondary outcomes, MAR data still yield valid estimates. Although not expected, if it appears that the MAR assumption is not reasonable, then we will invoke shared parameter models to simultaneously model the time to drop-out and the individual secondary outcome²⁸.

F. Interim Analyses

There will be no formal interim analysis of efficacy in this trial. Nevertheless, interim statistical analyses to evaluate the safety of the three treatment regimens will be presented to the AsthmaNet Data and Safety Monitoring Board (DSMB) semi-annually for review. Based on the results of these interim analyses, the DSMB will recommend to the NHLBI the continuation or discontinuation of the trial. In addition, the DSMB will be monitoring all of the safety data throughout the course of the trial and will be notified within 72 hours of any serious adverse event (SAE) that is deemed both unexpected and related to the study. All SAEs will be reviewed at each 6-month review.

G. Power Calculations

The target sample for the SIENA trial is 336 randomized participants, 74 in the eosinophilic phenotype and 262 in the non-eosinophilic phenotype, because we anticipate a 1-to-3.5 ratio, or smaller, of the eosinophilic phenotype to the non-eosinophilic phenotype.

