Risks: Participants in the study have persistent symptomatic asthma and will not receive regular inhaled corticosteroids during the 4-6 week Run-In Period and during 2 of the 3 three-month-long double-blind Treatment Periods. (All participants will, however, receive inhaled corticosteroids if their asthma control deteriorates). In addition, we believe that the "eosinophil negative" participants will not respond to inhaled corticosteroid treatment. It is therefore likely that a significant number of participants will experience deterioration of asthma control during the study. For this reason, we have defined a Treatment Failure status that we believe is sufficiently conservative that participants whose asthma control deteriorates will be "rescued" before they develop an asthma exacerbation. This rescue algorithm was used successfully in the NHLBI-ACRN IMPACT study³ - a comparison of daily versus "as-needed" ICS for mild persistent asthma. Participants who meet treatment failure status during the Run-in will be treated according to a rescue algorithm and will continue in the study. If necessary, the run-in will be extended so that ≥ 3 weeks elapse after TF before randomization. Participants with ≥ 2 TFs during the Run-In will be excluded from the double-blind Treatment Period. To provide an additional level of safety, we have added additional exclusion criteria at the end of the Run-In that must be met before participants can be randomized. Finally, TF criteria will also be used throughout the treatment period - to ensure the safety of participants.

We have designed the study with frequent study visits and phone visits (every 3 weeks) to allow for close monitoring of asthma control. All participants will be given an electronic diary/peak flow device at entry into the Run-In, which will provide objective data for assessment of control. Participants who do not adhere to this monitoring on 75% of days will not be permitted to proceed to the double-blind Treatment Period.

Participants who experience an Asthma Exacerbation will be treated with prednisone and seen at the clinic after 3 days to ascertain the severity of the event and ensure appropriate treatment. As part of our "characterization of asthma exacerbations", they will be evaluated in person or by phone on days 3, 10, 14, and 21.

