Respimat and an increased rate of deaths, a large long-term study of 17,135 patients with COPD was conducted. Analysis of the data from the trial concluded that tiotropium Respimat had a safety profile similar to tiotropium HandiHaler in patients with COPD, and was not associated with an increased risk of death.

Participants with history of urinary retention, elevated intraocular pressure, and significant cardiovascular disease will be excluded from the study.

An IND has been obtained from the FDA (#121996) for the SIENA study.

Benefits: Tiotropium has been shown to be not inferior to salmeterol as add-on treatment in asthma, and in a small study tiotropium increased FEV1 in asthmatics with low sputum eosinophil counts. Because all patients do not respond to inhaled corticosteroids, and some appear to have adverse effects associated with their use, there is a need for additional controller medications which can be used when inhaled corticosteroid does not provide adequate asthma control. If tiotropium bromide is found to be effective when used in this manner, important benefits to asthma patients would be anticipated.

The potential benefits justify the potential risks.

X. ADVERSE EVENTS

A. Definition and reporting

Participants are at risk of developing adverse events during study enrollment. A clinical adverse event is any unintended worsening in the structure (signs) or function (symptoms) of the body, whether or not considered to be

study-related. This includes any side effect, injury, or sensitivity reaction, as well as any intercurrent event. A laboratory adverse event is any clinically-important worsening in a test variable which occurs during the course of the study, whether or not considered to be drug-related. An adverse event is deemed serious if it suggests a significant hazard, contraindication, side effect, or precaution. Serious adverse events include any experience that is fatal or life-threatening, is permanently disabling, requires or prolongs inpatient hospitalization, or is a congenital anomaly, cancer, or overdose.

Documentation of an adverse event will be recorded on the Clinical Adverse Event Report Form and will include the following information: Description of the condition, dates of condition, treatment of condition (medications, doses, dates), whether hospitalization or emergency treatment was required, treatment outcome, relationship of the adverse event to the study medication(s), and severity of the event.

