B. Adverse Events Unrelated to Asthma

Adverse events due to concurrent illnesses other than asthma may be grounds for withdrawal if the illness is considered significant by the study investigator or if the participant is no longer able to effectively participate in the study. Participants experiencing minor intercurrent illnesses may continue in the study provided that the nature, severity, and duration of the illness are recorded and that any unscheduled medications required to treat the illness are also recorded. Examples of minor intercurrent illnesses include acute rhinitis, sinusitis, upper respiratory infections, urinary tract infections, and gastroenteritis.

Medications are allowed for treatment of these conditions in accordance with the judgment of the responsible study physician.

C. Adverse Events Related to Asthma: Treatment Failure and Asthma Exacerbation

Since participants have persistent symptomatic asthma and will not receive regular inhaled corticosteroids during the 4-6 week Run-In Period and during 2 of the 3 three-month long double-blind Treatment periods, we anticipate that asthma treatment failures will occur. Safety net procedures, including visits and frequent telephone contacts, are in place to identify participants who experience a treatment failure (a primary outcome) or asthma exacerbation during the study.

Between in-person study visits (as described above), participants will be contacted by telephone by the clinic coordinator to assure that they are continuing to participate appropriately in the study protocol, to answer any questions that may arise, and to assure that their asthma is under adequate control, as assessed by the participant. The coordinator will attempt to determine whether the participant is showing signs of treatment failure using specific criteria. If it is determined that the participant fulfills criteria for treatment failure, they will be advised to initiate high-dose ICS rescue treatment (i.e., mometasone 400-440 mcg BID, dose dependent on mometasone device randomized to at Visit 3 – See Appendix D x 10 days).

If, between phone contacts or in-person visits, an asthma exacerbation has occurred, the participant should contact the clinic coordinator and/or be

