Medical judgment should be used to determine the relationship, considering all relevant factors, including pattern of reaction, temporal relationship, de-challenge or re-challenge, confounding factors such as concomitant medication, concomitant diseases and relevant history. Assessment of causal relationship should be recorded in the case report forms and on each company's SAE form.

Yes: There is a reasonable causal relationship between the investigational product administered and the AE.

No: There is no reasonable causal relationship between the investigational product administered and the AE.

Worsening of the underlying disease or other pre-existing conditions

Worsening of the underlying disease or of other pre-existing conditions will be recorded as an (S)AE in the (e)CRF.

Changes in vital signs, ECG, physical examination, and laboratory test results

Changes in vital signs, ECG, physical examination and laboratory test results will be recorded as an (S)AE in the (e)CRF, if they are judged clinically relevant by the investigator.

Responsibilities for SAE reporting

The Sponsor shall report (i.e., from signing the informed consent onwards through the trial defined follow-up period) all SAEs and non-serious AEs which are relevant for a reported SAE by fax or other secure method using each company's SAE form to the company's Unique Entry Point in accordance with timeline specified below. The trial defined follow-up period ends on the date when the *Termination of Study Participation* case report form is completed and signed. This generally occurs at the final study visit (see section VI.E. above) unless the participant drops out of the study prior to the final visit.

- within two (2) business days upon receipt of initial and follow-up SAEs containing at least one fatal or immediately life-threatening event;
- within two (2) business days upon receipt of any other initial and follow-up SAEs.

BIPI Unique Entry Point:

Boehringer Ingelheim Pharmaceuticals, Inc.

[name]

[contact]

E-mail: [contact]

Merck Unique Entry Point:

[contact]

TEVA Unique Entry Point:

E-mail: [name]

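### Section VIII.F guarantees 72-hour DSMB notice only for SAEs judged both unexpected and related, so an asthma hospitalisation while ICS is withheld could have the next 6-month review as its only dated board review.

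*Combined protocol and SAP*

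**What the plan says.** Section VIII.F (Interim Analyses) gives the board three routes to safety information.

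- **Scheduled.** Safety analyses of the three regimens go to the DSMB twice a year, and "All SAEs will be reviewed at each 6-month review".
- **Event-driven.** The board "will be notified within 72 hours of any serious adverse event (SAE) that is deemed both unexpected and related to the study".
- **Ongoing.** The section also states that "the DSMB will be monitoring all of the safety data throughout the course of the trial". It attaches no interval, trigger or deadline to this.

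Section X.A counts as serious any event that "requires or prolongs inpatient hospitalization", so an asthma admission is an SAE.

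On what the protocol foresees, IX.B (Risks of Study Design) says of a design that withholds regular ICS: "It is therefore likely that a significant number of participants will experience deterioration of asthma control during the study". X.C adds that "we anticipate that asthma treatment failures will occur". X.E goes further along the same path. It directs admission when peak flow is at or below 40% of baseline after repeated albuterol, unless the physician judges otherwise. Between 40% and 65% it leaves admission to an individual decision.

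**The concern.** The 72-hour rule has the usual form for catching surprising drug toxicity. The risk that IX.B discusses at length is of another kind: asthma worsening because a standard controller is deliberately withheld. That risk is foreseen, and foreseeing it is what could take an event outside a rule that requires it to be unexpected. Failing one of the two conditions is enough to lose the guaranteed notice.

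At stake is timely oversight across participants. IX.B relies on treatment failure criteria that are meant to bring rescue before an exacerbation develops. An asthma admission is evidence that this may not have worked for that person. One site sees one case, and the board is the body placed to see several. Whether it hears within 3 days or at the next scheduled review depends on a classification that the protocol leaves open. Two sites could classify the same kind of event differently.

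**Working it through.** VIII.F states no figure to reproduce, and the point depends on no sample size, power or alpha value. The check is a reading of every provision on DSMB and SAE reporting, followed by simple time arithmetic.

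**Step 1: dated routes for an SAE.**

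| Provision | Recipient | Which SAEs | Deadline |
|---|---|---|---|
| VIII.F, event-driven | DSMB | Unexpected and related to the study | 72 hours |
| VIII.F, scheduled | DSMB | All | Each 6-month review |
| VIII.F, ongoing monitoring | DSMB | All safety data | None stated |
| Appendix E | Donating companies | All, from consent | 2 business days from receipt |

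The adverse event section (X.A to X.E) adds no notice to the board. The only other mention of the DSMB, in Appendix D, concerns the change of mometasone device.

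**Step 2: an asthma admission under the event-driven rule.**

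1. Serious? Yes, under X.A.
2. Unexpected? Open. IX.B, X.C and X.E foresee deterioration, treatment failure and possible admission, which supports a judgement of expected. No passage lists asthma hospitalisation as an expected event, and VIII.F does not define the term.
3. Related to the study? Open. VIII.F does not define this either. Its ordinary meaning could well include harm from withheld ICS.

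Notice within 72 hours is assured only if both 2 and 3 are answered yes.

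**Step 3: the difference in dated review.**

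- Trigger met: 72 h / 24 = 3 days.
- Trigger missed: up to 6 months, 365 / 2 = about 183 days, or 52 / 2 = 26 weeks.
- In treatment periods: 26 / 12 = about 2.2 of the 12-week periods.
- If SAEs fall evenly between reviews held on schedule (an assumption), the mean wait is 26 / 2 = 13 weeks.

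These are waits to the *dated* review. Ongoing monitoring could shorten them by an amount the documents do not state.

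**The case against.** The strongest reply is that the rule may already cover these events. Treatment failures are anticipated, but the rescue scheme is meant to act before an exacerbation, so an admission can fairly be called unexpected. Relatedness to the study is broader than relatedness to a study drug and can include withheld treatment. An asthma death or intubation would probably be judged to meet both conditions. The same sentence of VIII.F also commits the board to ongoing monitoring. The DSMB charter is not among the documents and may hold a stricter rule.

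Much of this stands. It shows that the gap is possible, not certain. It does not show that notice is assured, because each step relies on a reading that VIII.F does not fix.

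The reply is also right that participants are protected individually whichever way an event is classified. They have rescue ICS, prednisone, early crossover, a clinic visit at day 3 and follow-up calls (VI.D, X.D). Enrolment and randomisation criteria exclude the less stable patients. None of this informs the board.

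Three stronger readings are tempting, and the documents do not support them.

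- *Appendix E makes the answer unrelated.* Its causality question is whether "There is a reasonable causal relationship between the investigational product administered and the AE", which fits withheld ICS badly. But Appendix E is written for reporting to the donating companies, VIII.F does not refer to it, and the wording of the two differs. Its answer cannot be carried into the DSMB rule.
- *IX.B names severe asthma events as the main hazard.* It does not. It names deterioration of asthma control and ranks nothing.
- *The share of the trial spent off ICS measures the gap.* It measures exposure. It does not say how often an asthma SAE occurs or misses the trigger, and part of that time is on active tiotropium.

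**Conclusion.** The concern holds in limited form. The only event-driven DSMB notice with a deadline requires an SAE to be both unexpected and related, and that fits poorly with a risk the protocol itself foresees. An asthma hospitalisation could be judged expected. Its only dated board review would then be the next 6-month review, from days to about 26 weeks away, where a qualifying event has 3 days.

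A reader might infer that the board would not learn of an asthma admission for six months. The text does not say that. It neither forces the classification nor makes the 6-month review the board's first knowledge of an event, given the undated monitoring.

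The conclusion assumes that VIII.F is the operative rule and that no charter provision supersedes it. No event count is offered, because the documents give neither an asthma SAE rate nor a probability of missing the trigger. The point concerns safety oversight alone and has no bearing on the estimates, error rates or power. It is worth making because the remedy is cheap and goes beyond defining two terms: it takes the judgement out of the pathway for asthma SAEs.

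**What to change.** Extend the notification sentence in VIII.F so that the DSMB is told within 72 hours of:

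- (a) any SAE deemed both unexpected and related to the study, as now; and
- (b) any asthma-related SAE (hospitalisation, intubation or death) from consent onward, regardless of expectedness or relatedness.

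Consent means Visit 0A for supervised-washout participants and Visit 1 for the others, so washout and run-in are covered. Keep the 6-month review of all SAEs and the board's advisory role unchanged.

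The cost is one or two sentences and some additional notices to the board; how many cannot be estimated from the documents. No new data collection is needed. Appendix E already has worsening of the underlying disease recorded as an adverse or serious adverse event, and SAEs sent to the donating companies within two business days of receipt. If the DSMB charter already contains this rule, VIII.F need only state it.

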Asthma-Specific Work Productivity and Activities Impairment Questionnaire (WPAI:Asthma)								X				X			X					X	
Home Environment Questionnaire (HEQ)						X															
Household Socio-Economic Information questionnaire (HOUSEHOLD_SEI)						X															
Perceived Stress Scale (PSS)							X														
Sinonasal Questionnaire (SNQ)							X				X			X			X			X	
Impact of Asthma on Quality of Life (IAQL) ³¹							X				X			X			X			X	
Acute Asthma Assessment Questionnaire (AAAQ)							X														X
Review electronic diary	X	X			X		X		X		X		X		X		X		X		X
Review medication use					X		X		X		X		X		X		X		X		X
Satisfaction questionnaire																					X
Treatment failure assessment					X		X		X		X		X		X		X		X		X
Dispense e-diary/PEF meter	X		X ³																		
Dispense run-in medications (placebo LMA)			X ³		X																
Dispense open label “high-dose” ICS for Treatment Failure			X ³																		
Dispense rescue prednisone supply	X		X ³																		
Dispense randomized medication							X		X		X		X		X		X		X		
50% reduction in ICS dose	X																				
Discontinuation of ICS if well-controlled		X																			

¹ For those taking ICS or ICS/LABA intermittently, low-dose ICS, or LTRA

² Genetics blood sample is optional

³ Done at V1A if participant does not qualify by Reversibility

⁴ Methacholine challenge ONLY done (at V1A) if participant does not qualify by Reversibility

⁵ If Sputum Induction necessary for eligibility at V3, these procedures will be performed at an additional visit (V2A) at least 1 week prior to V3

[figure not shown]
⁶ Reversibility testing done to qualify for sputum induction

⁷ Includes WPAI:Asthma, Wisconsin Upper Respiratory Symptom Score – 21 (WURSS-21) and AAAQ

⁸ 2-Step Washout participants have Visit 0A at -5 weeks and Visit 0B at -3 weeks; 1-Step Washout participants have Visit 0A at -3 weeks and skip Visit 0B

B. List of Asthma Questionnaires to be used

SIENA: Schematic

C. Draft Acute Asthma Assessment Questionnaire

AsthmaNet

**ACUTE ASTHMA
ASSESSMENT
QUESTIONNAIRE**

Part. ID: _____
Part. Initials: _____
Visit: _____
Visit Date: ____ / ____ / 20 ____
Coordinator ID: _____

(Participant Completed)

Please check only one box for each question.

1. In the past 3 days , how much of the time did your asthma keep you from doing your usual activities at work, school, or at home?	(1000)	 0 None of the time  1 A little of the time  2 Some of the time  3 Most of the time  4 All of the time
2. During the past 3 days , how often have you had asthma symptoms? Asthma symptoms include wheezing, coughing, shortness of breath, chest tightness or pain, phlegm or mucus.	(1010)	 0 Not at all  1 Once per day  2 2-3 times per day  3 4-5 times per day  4 6 or more times per day
3. During the past 3 days , how often have you used your rescue inhaler or nebulizer medication (such as albuterol)?	(1020)	 0 Not at all  1 Once per day  2 2-3 times per day  3 4-5 times per day  4 6 or more times per day
4. During the past 3 days , how many total times did your asthma symptoms wake you up from sleep? Asthma symptoms include wheezing, coughing, shortness of breath, chest tightness or pain, phlegm or mucus.	(1030)	 0 Not at all  1 1 time in the last 3 days  2 2-3 times in the last 3 days  3 4-5 times in the last 3 days  4 ≥6 times in the last 3 days
5. How would you rate the amount of impairment you have experienced due to your asthma in the past 3 days ?	(1040)	 0 No impairment  1 Mild impairment  2 Moderate impairment  3 Severe impairment  4 Very severe impairment
6. How stressed or frightened were you by your asthma symptoms in the past 3 days ?	(1050)	 0 Not at all  1 Mildly  2 Moderately  3 Severely  4 Very severely

7. Why do you think your asthma was worse in the past 3 days compared to what is normal for you? Pick the main reason. There is no right or wrong answer. We want your opinion. (1060)

₀ I have not been worse over the past 3 days. My asthma symptoms have been usual.
 ₁ Common cold
 ₂ Allergies
 ₃ Pollution or chemical irritant
 ₄ Too little asthma maintenance medication
 ₅ Exercise
 ₆ Other (specify) _____

(1060D) _____

D. Study Drug Procurement and Distribution

All pharmaceutical companies that manufacture long-acting muscarinic antagonists and inhaled corticosteroids were invited to participate in SIENA by providing active drug and placebo for the study.

Long-Acting Muscarinic Antagonist and Placebo: *Boehringer Ingelheim* has agreed to provide tiotropium, in the form of tiotropium Respimat, 2.5 mcg per actuation and tiotropium placebo. Participants will take 2 puffs each day (total dose active drug = 5mcg). *Boehringer Ingelheim* will coordinate the blinding and labeling of drug with input and assistance from the DCC.

Inhaled Corticosteroid and Placebo: *Merck* has agreed to provide mometasone and mometasone placebo. Mometasone will be in the form of Asmanex® DPI, 110 mcg/puff. Participants will take 2 puffs twice daily (total dose active drug = 440 mcg). *Merck* will coordinate the blinding of drug with information provided by the DCC. A third-party packager will label with additional regulatory information.

Production of mometasone DPI was discontinued shortly after SIENA study start following FDA approval of mometasone MDI. Since this was a known possibility, Merck provided AsthmaNet all available active and placebo mometasone DPI devices in 2014 with the goal of providing sufficient quantities to complete the SIENA protocol. However, Merck agreed to provide additional mometasone in MDI form if that became necessary to complete SIENA.

While the quantity of DPI product provided is adequate to complete SIENA, product expiration will become a problem if SIENA recruitment lags. Limited quantities of active mometasone DPI are available with expiration dating beyond November 2016, and those limited quantities have an expiration of April 2017. Thus, if recruitment is not completed by May 2016, then a switch to MDI product will be required. Based on drug availability, a switch to MDI cannot be made earlier than November 2015.

The AsthmaNet Steering Committee will monitor SIENA recruitment and continually reevaluate the likelihood of completing recruitment by May 2016. Depending on the results of this evaluation, the Steering Committee may recommend to the DSMB that a switch to MDI should be made. If a switch is made, all participants will complete the study using whichever formulation they receive at randomization. No participants will switch from DPI to MDI during the course of the study. The randomization plan and the statistical analysis plan will be modified accordingly. In particular, we will insert an additional level of stratification for randomization according to DPI/MDI assignment. The current statistical plan is to include the stratifying variables as blocking factors, so DPI/MDI assignment will be included as a blocking factor in the statistical

analysis.

Update November 2015: Due to lagging recruitment and mometasone DPI expiration issues, a switch to mometasone MDI is necessary. *Merck* has provided mometasone and mometasone placebo in the form of Asmanex® HFA, 200 mcg/puff. Participants will take 1 puff twice daily (total dose active drug = 400 mcg). *Merck* will coordinate the blinding of drug with information provided by the DCC. A third-party packager will label with additional regulatory information.

Contingent Statistical Analysis

Because SIENA invokes a three-way crossover design, a stratified randomization based on prognostic factors is not critical. Instead, we only will invoke clinical site within phenotype (eosinophilic, non-eosinophilic) as a stratifying variable with permuted blocks of size six (one complete cycle of the six). As indicated above, if a DPI/MDI switch occurs, then we will include this as another stratification variable. In particular, the stratification will be according to DPI/MDI status nested within clinical center, which is nested within phenotype.

The statistical analysis plan for the primary and secondary outcomes is described in Section VIII.C. With respect to the primary outcome variable, we will apply a linear mixed-effect model that includes (1) fixed effects for treatment regimen, sequence, period, and season of enrollment (spring, summer, fall, winter) nested within each of the eosinophilic and non-eosinophilic phenotypes, (2) random effects for clinical site within each of the eosinophilic and non-eosinophilic phenotypes, and (3) a 7×7 unstructured variance-covariance matrix for the seven measurements per participant within each of the eosinophilic and non-eosinophilic phenotypes. We will account for the additional stratifying variable of DPI/MDI status by including it as another fixed-effect variable in linear mixed-effects model.

Obviously, completion of the entire study with the same manufacturer's lot of active drug and placebo is ideal. However, if *Merck* is not able to provide us with sufficient placebo DPI, we do not believe that the switch from active DPI to active MDI will negatively impact the scientific validity of the study.

The goal of the study is to examine whether subjects with *mild-to-moderate asthma* who are persistently non-eosinophilic require a different treatment strategy than those with sputum eosinophilia. Preliminary data suggest that subjects without sputum eosinophilia (presumed "TH2-low" asthma) do not respond to inhaled corticosteroids or to prednisone. In SIENA we will enroll subjects with persistent asthma who meet the EPR-3 criteria for *Mild-to-Moderate Asthma* and for whom *Step 2 Treatment* (Preferred = Low-dose ICS) is recommended. However, because we believe that ~50% of these subjects will not respond to ICS, we will provide *Step 3 Treatment* (Medium-dose ICS), to ensure that the issue is not too little ICS. In the case of Mometasone, EPR-3

defines "low-dose" as 200 mcg/day and "medium dose" as 400 mcg/day. Because Merck will be fulfilling FDA criteria for equivalence, we anticipate that the doses delivered will be comparable, but even if there is a small difference in dose delivered between the DPI and MDI preparations, that dose should be sufficiently high on the flat portion of the dose-response curve that it will not impact the outcome.

High-dose Inhaled Corticosteroid for Treatment Failure: Merck has agreed to provide open-label mometasone (Asmanex® DPI, 220 mcg/puff) for use as high-dose Inhaled Corticosteroid Rescue for participants who experience Treatment Failure.

Update November 2015: Merck has agreed to provide open-label mometasone MDI (Asmanex® HFA, 200 mcg/puff) for use as high-dose Inhaled Corticosteroid Rescue for participants who experience Treatment Failure.

Albuterol for Rescue: TEVA has agreed to provide open label albuterol (Pro-Air® HFA, 90 mcg albuterol/puff) as bronchodilator rescue for the study.

E. Adverse Event Reporting to Companies Donating Study Drug

Adverse event

An adverse event (AE) is defined as any untoward medical occurrence, including an exacerbation of a pre-existing condition, in a patient in a clinical investigation who received a pharmaceutical product. The event does not necessarily have to have a causal relationship with this treatment.

Serious adverse event

A serious adverse event (SAE) is defined as any AE which results in death, is immediately life-threatening, results in persistent or significant disability / incapacity, requires or prolongs patient hospitalisation, is a congenital anomaly / birth defect, or is to be deemed serious for any other reason if it is an important medical event when based upon appropriate medical judgement which may jeopardise the patient and may require medical or surgical intervention to prevent one of the other outcomes listed in the above definitions.

Patients may be hospitalised for administrative or social reasons during the study (e.g. days on which infusion takes place, long distance from home to site,). These and other hospitalisations planned at the beginning of the study do not need to be reported as a SAE in case they have been reported at screening visit in the source data and have been performed as planned.

Intensity of adverse event

The intensity of the AE should be judged based on the following:

- Mild: Awareness of sign(s) or symptom(s) which is/are easily tolerated
- Moderate: Enough discomfort to cause interference with usual activity
- Severe: Incapacitating or causing inability to work or to perform usual activities

Causal relationship of adverse event

Medical judgment should be used to determine the relationship, considering all relevant factors, including pattern of reaction, temporal relationship, de-challenge or re-challenge, confounding factors such as concomitant medication, concomitant diseases and relevant history. Assessment of causal relationship should be recorded in the case report forms and on each company's SAE form.

Yes: There is a reasonable causal relationship between the investigational product administered and the AE.

No: There is no reasonable causal relationship between the investigational product administered and the AE.

Worsening of the underlying disease or other pre-existing conditions

Worsening of the underlying disease or of other pre-existing conditions will be recorded as an (S)AE in the (e)CRF.

Changes in vital signs, ECG, physical examination, and laboratory test results

Changes in vital signs, ECG, physical examination and laboratory test results will be recorded as an (S)AE in the (e)CRF, if they are judged clinically relevant by the investigator.

Responsibilities for SAE reporting

The Sponsor shall report (i.e., from signing the informed consent onwards through the trial defined follow-up period) all SAEs and non-serious AEs which are relevant for a reported SAE by fax or other secure method using each company's SAE form to the company's Unique Entry Point in accordance with timeline specified below. The trial defined follow-up period ends on the date when the *Termination of Study Participation* case report form is completed and signed. This generally occurs at the final study visit (see section VI.E. above) unless the participant drops out of the study prior to the final visit.

- within two (2) business days upon receipt of initial and follow-up SAEs containing at least one fatal or immediately life-threatening event;
- within two (2) business days upon receipt of any other initial and follow-up SAEs.

BIPI Unique Entry Point:

Boehringer Ingelheim Pharmaceuticals, Inc.

[name]

[contact]

E-mail: [contact]

Merck Unique Entry Point:

[contact]

TEVA Unique Entry Point:

E-mail: [name]

For each adverse event, the investigator will provide the onset date, end date, intensity, treatment required, outcome, seriousness, and action taken with the investigational drug. The investigator will determine the expectedness of the investigational drug to the AEs as defined in the Listed or BI Drug Information e.g. Summary of Product Characteristics (SmPC) or Product Information (PI) for the authorised Study Drug provided by BI [Boehringer Ingelheim, Investigator's Brochure, Doc. No: U92-0551-19, pp 195-200, July 13, 2012].

F. EPR-3 Table 4-8b

FIGURE 4-8b. ESTIMATED COMPARATIVE DAILY DOSAGES FOR INHALED CORTICOSTEROIDS FOR YOUTHS ≥ 12 YEARS OF AGE AND ADULTS

Drug	Low Daily Dose Adult	Medium Daily Dose Adult	High Daily Dose Adult
Beclomethasone HFA 40 or 80 mcg/puff	80–240 mcg	>240–480 mcg	>480 mcg
Budesonide DPI 90, 180, or 200 mcg/inhalation	180–600 mcg	>600–1,200 mcg	>1,200 mcg
Flunisolide 250 mcg/puff	500–1,000 mcg	>1,000–2,000 mcg	>2,000 mcg
Flunisolide HFA 80 mcg/puff	320 mcg	>320–640 mcg	>640 mcg
Fluticasone HFA/MDI: 44, 110, or 220 mcg/puff DPI: 50, 100, or 250 mcg/inhalation	88–264 mcg 100–300 mcg	>264–440 mcg >300–500 mcg	>440 mcg >500 mcg
Mometasone DPI 200 mcg/inhalation	200 mcg	400 mcg	>400 mcg
Triamcinolone acetonide 75 mcg/puff	300–750 mcg	>750–1,500 mcg	>1,500 mcg

Key: DPI, dry powder inhaler; HFA, hydrofluoroalkane; MDI, metered-dose inhaler

Notes:

- The most important determinant of appropriate dosing is the clinician's judgment of the patient's response to therapy. The clinician must monitor the patient's response on several clinical parameters and adjust the dose accordingly. The stepwise approach to therapy emphasizes that once control of asthma is achieved, the dose of medication should be carefully titrated to the minimum dose required to maintain control, thus reducing the potential for adverse effect.
- Some doses may be outside package labeling, especially in the high-dose range.
- MDI dosages are expressed as the actuator dose (the amount of the drug leaving the actuator and delivered to the patient), which is the labeling required in the United States. This is different from the dosage expressed as the valve dose (the amount of drug leaving the valve, not all of which is available to the patient), which is used in many European countries and in some scientific literature. DPI doses are expressed as the amount of drug in the inhaler following activation.
- Comparative dosages are based on published comparative clinical trials (Adams et al. 2005; Barnes et al. 1998; Kelly 1998; Lasserson et al. 2005; Pedersen and O'Byrne 1997). The rationale for some key comparisons is summarized as follows:
 - The high dose is the dose that appears likely to be the threshold beyond which significant hypothalamic-pituitary-adrenal (HPA) axis suppression is produced, and, by extrapolation, the risk is increased for other clinically significant systemic effects if used for prolonged periods of time (Martin et al. 2002; Szefler et al. 2002).
 - The low- and medium-doses reflect findings from dose-ranging studies in which incremental efficacy within the low- to medium-dose ranges was established without increased systemic effect as measured by overnight cortisol excretion. The studies demonstrated a relatively flat dose-response curve for efficacy at the medium-dose range; that is, increasing the dose of high-dose range did not significantly increase efficacy but did increase systemic effect (Adams et al. 2001; Martin et al. 2002; Szefler et al. 2002).
 - The doses for budesonide and fluticasone MDI or DPI are based on recently available comparative data. These new data, including meta-analyses, show that fluticasone requires one-half the microgram dose of budesonide DPI to achieve comparable efficacy (Adams et al. 2005; Barnes et al. 1998; Nielsen and Dahl 2000).
